Subjects may choose to allow future use of remaining samples in the informed consent form. After all tests are completed, any leftover samples will be saved for future research studies on HPV. The blood, cell, oral, and stool samples will be frozen and will be stored with only the subject identifier. The cell samples may be stored indefinitely until needed for a future research study. Subjects who originally chose to allow future use of remaining samples but change their mind later may notify the PI in writing to the address listed in the informed consent form. The subject identifier will be linked to the subject's name and the study team will collect the sample and destroy it per institutional guidelines.

LABORATORY EVALUATIONS

BLOOD SAMPLES

Complete blood count with differential, Chem 7, and liver function tests will be performed at [INSERT LOCAL LAB] in accordance with their current SOPs.

FACS ANALYSIS

Peripheral blood mononuclear cells (PBMCs) isolated from blood samples drawn at Visits 1, 5, 8, and 9 may be analyzed at UAMS to measure circulating immune cells such as Th1, Th2, regulatory T-cell (Treg), and myeloid-derived suppressor cells (MDSCs). HLA typing may be performed using remaining PBMCs.

ELISPOT

An immune assay such as an ELISPOT assay to assess the presence of HPV-specific T-cells will be performed. After each blood draw, PBMCs will be separated into CD14+ and CD14- populations and cryopreserved. To eliminate inter-assay variability, all 4 blood samples (before vaccination, after 4 vaccinations, 7 vaccinations, and at the end of the study) will be used to establish T-cell lines and to

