Extraction of microbial DNA will be performed at UAMS using the MoBio PowerFecal DNA Isolation Kit (QIAGEN, Cat. No. 12830-50, California) or ZymoBioMICS DNA Miniprep Kit (Zymo Research Cat. No. D4300, Irvine, California). Quality of isolated DNA samples may be determined by agarose gel image and OD 260/280 ratio (OD 260/280 = 1.8^{2} .0). Microbiome diversity analysis may be performed in two methods - Illumina MiSeq/HiSeq and MiniON Flow Cell. For research purposes only, the UAMS bioinformatics researchers will evaluate the quality of data acquisition between two methods of DNA sequencing and provide the microbiome profiling data of DNAs in the fecal samples from subjects with head and neck cancer.

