8.2 STATISTICAL ANALYSES

Subjects who received at least one dose of the vaccine will be included in safety assessments. Safety analyses will include summaries of the incidence of AEs using the NCI CTCAE Version 5.0 that occur during the study period regardless of causality. The AEs will be mostly descriptive initially. However, after unblinding at the completion of the study, rates of common side effects (occurring with 5% or more injections) will be compared between the PepCan and the placebo arms. Efficacy will be assessed by comparing cancer recurrence rate between the 2 arms. The expected number of head and neck cancer patients who achieve remission is 100 patients per year. For immunological assessments, the presence of new anti-HPV-16 E6 T-cell activity will be measured using CD3 ELISPOT assay, and its statistical significance will be assessed using a paired *t*-test. For analyses of immune cells such as Th1, Th2, Treg, and MDSCs, percentages before and after vaccination will also be assed using a two-tailed paired *t*-test. The frequencies between subjects who experience recurrence and those that do not in the PepCan arm will be compared using Wilcoxon rank-sum test. The diversity of gut microbiome will be assessed prior to

injection, and will be compared to that after injection using alpha diversity, beta diversity, and compositions at the phylum or family levels. These parameters will also be compared between subjects with and without recurrence with in the PepCan arm.

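### The microbiome and FACS before/after comparisons are not protected against a change of kit, platform or run between a subject's early and late samples, and the placebo arm is not used to remove it

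*Combined protocol and SAP*

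**What the plan says.** **Microbiome.** In Section 7.3, under DNA sequencing of oral wash and stool samples, extraction is to use the "MoBio PowerFecal DNA Isolation Kit (QIAGEN, Cat. No. 12830-50, California) or ZymoBioMICS DNA Miniprep Kit". No rule says which samples get which kit. On sequencing, "Microbiome diversity analysis may be performed in two methods - Illumina MiSeq/HiSeq and MiniON Flow Cell". The next sentence adds that the bioinformatics team "will evaluate the quality of data acquisition between two methods of DNA sequencing". No platform is named as the source of the analysed data. Samples are taken at Screening and Visits 5, 7 and 8.

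**ELISPOT.** The same section gives a safeguard: "To eliminate inter-assay variability, all 4 blood samples (before vaccination, after 4 vaccinations, 7 vaccinations, and at the end of the study" are used to set up the T-cell lines and run the assays. It does not literally say that they share one run, but the stated purpose points that way.

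**FACS.** Cells from Visits 1, 5, 8 and 9 "may be analyzed at UAMS to measure circulating immune cells such as Th1" and other subsets. No matching sentence on inter-assay variability appears here, or for the optional cytokine panel.

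**Analysis.** Section 8.2 states: "The diversity of gut microbiome will be assessed prior to" injection and compared with the result after injection, by alpha diversity, beta diversity and composition. No test is named. Immune-cell percentages before and after vaccination get a two-tailed paired t-test. The only between-group comparison for either measure is recurrence against no recurrence inside the PepCan arm.

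**The concern.** In a before/after test, visit order and calendar time run together. If samples are assayed as they arrive, a new kit, reagent lot, instrument setting or platform puts late samples under the new condition more often than early ones. The resulting shift acts as a bias in the mean change, not only as noise, and a within-subject test cannot separate it from biology.

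The protocol accepts this hazard for ELISPOT but not for FACS, although Section 3 places the two under the same tertiary objective. FACS also matters to the rationale: Section 2.3 justifies seven doses by a wish to prolong the Th1 shift, and Th1 percentage is a FACS measure. The trial has a randomised placebo arm on the same sampling schedule, which could absorb drift common to both arms, but Section 8.2 does not use it for these measures.

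**Working it through.** The plan states no figure for assay variability, so there is nothing of its own to reproduce. The check has three parts.

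**1. Time between samples** (intervals from Sections 7.1 and 11.1, visit windows ignored, 30.44 days per month)

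- Visit 1 to Visit 4: 3 × 21 = 63 days = 2.1 months.
- Visit 5: 2.1 + 3 = 5.1 months. Visit 7: 5.1 + 3 + 3 = 11.1. Visit 8: 11.1 + 6 = 17.1. Visit 9: 17.1 + 6 = 23.1.
- FACS, Visit 1 to Visit 9: about 23 months.
- Microbiome, Screening to Visit 8: about 17 months, or 17.1 + 90 days (3.0 months) = about 20 months if the whole 90-day screening window is used.

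**2. False-positive rate of the FACS paired t-test with no vaccine effect**

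Inputs: n = 75, the planned PepCan arm (Section 8.1; Section 8.2 does not name the arm), and a two-tailed test. The 5% level is taken from the recurrence design. Two quantities are assumed: the shift d, in SD units of the within-subject change, and the fraction f of subjects whose early and late samples fall on opposite sides of the change.

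The mean change is f·d, and its SD is √(1 + f(1 − f)d²). The noncentrality is √n · f·d / √(1 + f(1 − f)d²), referred to a noncentral t on 74 degrees of freedom with critical value 1.993.

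Examples at d = 0.3, with √75 = 8.660:
- f = 1: 8.660 × 0.3 = 2.598, giving 72.7%.
- f = 0.5: 8.660 × 0.15 / √1.0225 = 1.285, giving 24.5%.
- f = 0.25: 8.660 × 0.075 / √1.0169 = 0.644, giving 9.7%.

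| Shift d | f = 1 | f = 0.5 | f = 0.25 |
|---|---|---|---|
| 0.1 | 13.7% | 7.1% | 5.5% |
| 0.2 | 40.1% | 13.6% | 7.1% |
| 0.3 | 72.7% | 24.5% | 9.7% |

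A simulation of the f = 0.5 and f = 0.25 columns agrees to within 0.1 percentage point.

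Fewer subjects may reach Visit 9, because recurrence ends participation (Section 5.5). With the design recurrence rate of 44%, 75 × 0.56 = 42 remain. With f = 1 the rates are then 9.7%, 24.4% and 47.6%.

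**3. What removes the shift**

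- If all of a subject's time points share the kit, platform and run, the shift cancels within the subject and the rate returns to 5%.
- If change is compared between arms and the shift is common to both, it cancels in the difference. Simulated at d = 0.3 and f = 1 with 72 and 24 subjects, the between-arm t-test rejects in 5.0% of trials and the within-arm test in 71%.
- The between-arm comparison is less precise: its standard error is √(1/75 + 1/25) = 0.231 SD, against 1/√75 = 0.115 SD within the PepCan arm, a factor of two.

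**The case against.** **The two platforms are there to be compared.** This largely stands. A reader might infer that early samples go to one platform and late samples to the other. The sentence on evaluating data quality makes parallel use the more natural reading, so such mixing is permitted by silence, not planned. What remains is that no platform is named for the before/after data, and that the choice between kits has no such explanation.

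**The large error rates are a worst case.** This stands too. A reader might take 14%, 40% and 73% as the expected rates, but they require every subject to straddle the change. Enrolment is staggered, so a change on one calendar date affects only subjects who are between samples on that date. The rates also belong to the FACS t-test: Section 8.2 names no test for the microbiome and no analysis at all for cytokines, so they cannot be carried over.

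**Drift would show in the placebo arm.** The data for that would exist, but Section 8.2 plans no such comparison.

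**The endpoints are minor and batching belongs in a laboratory manual.** FACS and cytokines are worded as optional, FACS is tertiary and the microbiome is exploratory. That sets the priority. It does not explain why ELISPOT alone has its safeguard in the protocol.

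**Conclusion.** The point holds in a conditional form. Section 7.3 leaves the extraction kit open and the analysis platform unnamed, and gives neither the microbiome nor the FACS assays the protection given to ELISPOT. Since Section 8.2 sets out no comparison with placebo for these measures, a method change falling between early and late samples would be indistinguishable from a vaccine effect.

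The size cannot be known from the documents. Over the assumed ranges, the FACS false-positive rate runs from 5.5% (0.1 SD, a quarter of subjects affected) to 73% (0.3 SD, all affected), against a nominal 5%. Both the shift and the fraction affected are assumptions.

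The documents do not show that any change of method is planned or has occurred. The primary safety analysis and the secondary recurrence analysis do not depend on these assays. Minor priority; a cheap improvement.

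**What to change.** **Section 7.3**
- Name one extraction kit and one sequencing platform for the analysed microbiome data set. Keep the second platform for the method comparison only.
- Process each subject's time points in the same run wherever samples can be stored, with both arms mixed across runs under coded labels.
- State whether FACS uses frozen or fresh cells. If fresh, include a common reference sample in every run and adjust for run.
- Apply the same rule to plasma if the cytokine panel is run.

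**Section 8.2**
- Add a comparison of change from baseline between PepCan and placebo for FACS and microbiome measures. This removes drift common to both arms. Keep the within-arm comparison as descriptive support.

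**Cost.** No new visits, subjects or specimens. Results come later, after a subject's last sample. With about 25 placebo subjects the between-arm estimate is about half as precise as the within-arm one. Storage has to be confirmed: cryopreservation is stated only for the separated CD14+ and CD14- cells under ELISPOT, and the text on frozen blood, cell, oral and stool samples concerns leftovers after testing. Nothing says that plasma or unextracted stool is held until the last visit.

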7.4 ADVERSE EVENTS AND SERIOUS ADVERSE EVENTS

DEFINITION OF ADVERSE EVENTS (AES)

Adverse event means any untoward medical occurrence associated with the use of an intervention in humans, whether or not considered intervention-related (21 CFR 312.32 (a)).

DEFINITION OF SERIOUS ADVERSE EVENTS (SAES)

An AE or suspected adverse reaction is considered "serious" if, in the view of either the investigator or sponsor, it results in any of the following outcomes: death, a life-threatening AE, inpatient hospitalization or prolongation of existing hospitalization, a persistent or significant incapacity or substantial disruption

of the ability to conduct normal life functions, or a congenital anomaly/birth defect. Important medical events that may not result in death, be life-threatening, or require hospitalization may be considered serious when, based upon appropriate medical judgment, they may jeopardize the subject and may require medical or surgical intervention to prevent one of the outcomes listed in this definition.

To avoid confusion, as the terms "serious" and "severe" are not synonymous, the following clarification is given: The term "severe" is often used to describe the intensity (severity) of a specific event (as in mild, moderate or severe myocardial infarction); the event itself, however, may be of relatively minor medical significance (such as severe headache). This is *not* the same as "serious," which is based on subject/event *outcome* or *action* usually associated with events that pose a threat to a subject's life or functioning. Seriousness (not severity) serves as a guide for defining regulatory reporting obligations. [ICH-E2A(II)(B)]

CLASSIFICATION OF AN ADVERSE EVENT

SEVERITY OF EVENT

AEs will be graded using the NCI CTCAE Version 5.0. A copy of the NCI CTCAE Version 5.0 can be downloaded from the Cancer Therapy Evaluation Program (CTEP) home page. All appropriate treatment areas have access to a copy of the NCI CTCAE Version 5.0.

RELATIONSHIP TO STUDY INTERVENTION

All AEs must have their relationship to study intervention assessed by the clinician who examines and evaluates the subject based on temporal relationship and his/her clinical judgment. The degree of certainty about causality will be graded using the categories below. In a clinical trial, the study product must always be suspect.

- Definitely Related There is clear evidence to suggest a causal relationship, and other possible contributing factors can be ruled out. The clinical event, including an abnormal laboratory test result, occurs in a plausible time relationship to study intervention administration and cannot be explained by concurrent disease or other drugs or chemicals. The response to withdrawal of the study intervention should be clinically plausible. The event must be pharmacologically or phenomenologically definitive, with use of a satisfactory rechallenge procedure if necessary.
- Probably Related There is evidence to suggest a causal relationship, and the influence of other factors is unlikely. The clinical event, including an abnormal laboratory test result, occurs within a reasonable time after administration of the study intervention, is unlikely to be attributed to concurrent disease or other drugs or chemicals, and follows a clinically reasonable response on withdrawal (dechallenge). Rechallenge information is not required to fulfill this definition.
- Possibly Related There is some evidence to suggest a causal relationship (e.g., the event occurred within a reasonable time after administration of the trial medication). However, other factors may have contributed to the event (e.g., the subject's clinical condition, other concomitant events). Although an AE may rate only as "possibly related" soon after discovery, it can be flagged as requiring more information and later be upgraded to "probably related" or "definitely related", as appropriate.
- Unlikely to be related A clinical event, including an abnormal laboratory test result, whose temporal relationship to study intervention administration makes a causal relationship improbable (e.g., the event did not occur within a reasonable time after administration of the study intervention) and in which other drugs or chemicals or underlying disease provides plausible explanations (e.g., the subject's clinical condition, other concomitant treatments).

• Not Related - The AE is completely independent of study intervention administration, and/or evidence exists that the event is definitely related to another etiology. There must be an alternative, definitive etiology documented by the clinician.

EXPECTEDNESS

The local site PI or a local site Sub Investigator will be responsible for determining whether an AE is expected or unexpected. Vaccine-related or possibly vaccine-related AEs, which occurred with ≥5% of injections, in the order of decreasing number of occurrences, were injection-site reaction (immediate and delayed), myalgia, headache, nausea, fatigue, hypokalemia, fever, and flu-like symptoms [36, 37]. None of these AEs was more than grade 2. An AE will be considered unexpected if the nature, severity, or frequency of the event is not consistent with the risk information previously described for the study intervention.

TIME PERIOD AND FREQUENCY FOR EVENT ASSESSMENT AND FOLLOW-UP

The occurrence of an AE or SAE may come to the attention of study personnel during study visits and interviews of a study subject presenting for medical care, or upon review by a study monitor.

All AEs occurring during the study period must be recorded. The clinical course of each event should be followed until resolution, stabilization, or until it has been determined that the study treatment or participation is not the cause. SAEs that are still ongoing at the end of the study period must be followed for up to 30 days to determine the final outcome. Any SAE that occurs after the study period and is considered to be possibly related to the study treatment or study participation should be recorded and reported immediately to the Sponsor.

Multi-sites will capture adverse event source documentation within their electronic medical record system. Information to be collected may include event description, time of onset, clinician's assessment of severity, relationship to study product (assessed only by those with the training and authority to make a diagnosis), and time of resolution/stabilization of the event. All AEs occurring while on study must be documented appropriately regardless of relationship. All AEs will be followed to adequate resolution or to study termination. Additionally, the main site will document AEs in AR-AERS and the external sites will document AEs on a provided AE Log to ensure that all information is captured uniformly across multi-sites. All AEs including local and systemic reactions not meeting the criteria for SAEs will be captured on the appropriate electronic Case Report Form (eCRF) in OpenClinica (OC).

Any medical condition that is present at the time that the subject is screened will be considered as baseline and not reported as an AE. However, if the study subject's condition deteriorates or exacerbates at any time during the study, it will be recorded as an AE.

Changes in the severity of an AE will be documented to allow an assessment of the duration of the event at each level of severity to be performed. AEs characterized as intermittent require documentation of onset and duration of each episode.

Study staff responsible for reporting AEs will be listed on the Delegation Log and will record all reportable events with start dates occurring any time after informed consent has been obtained until the end of study participation. At each study visit, the investigator, or a designee, will inquire about the occurrence of

AEs/SAEs since the last visit. Events will be followed for outcome information until resolution or stabilization.

A summary of AEs will be included in the annual IRB status report and the IND report to the FDA.

SERIOUS ADVERSE EVENT REPORTING

A serious, unexpected (previously not expected in nature, severity, or degree of incidence), and drug-related AE must be reported to:

- ORRA and UAMS PI within 24 hours of local site PI being notified.
- The FDA will be notified using the MedWatch Form FDA 3500A within 10 days of local site PI being notified. The local site PI will report to ORRA and UAMS PI; ORRA will report to FDA.
- The UAMS IRB will be notified of events requiring expedited reporting within 10 days of local site PI being notified (see below if SAE is death).
- A drug-related death or event that is considered life-threatening occurring while a subject is on the study must be reported to the UAMS IRB immediately and to the FDA within 7 days of the investigator learning of the event.
- THE CAUSE OF DEATH AND THE INVESTIGATOR'S DISCUSSION REGARDING WHETHER OR NOT THE DEATH WAS DRUG-RELATED SHOULD BE DESCRIBED IN A WRITTEN REPORT.

7.5 ELECTRONIC DATA CAPTURE

OPENCLINICA

OpenClinica (OC) is an open source clinical trial software platform and will be the Electronic Data Capture (EDC) for this study's clinical data management. OC will be the main platform for external sites to report data to the main site. External sites will register subjects to the study through OC. Multi-sites will capture source documentation within their electronic medical record system and report all necessary safety and clinical data to the main site by completing the appropriate eCRFs.

7.6 QUESTIONNAIRES

DEMOGRAPHICS AND CONTACT INFORMATION FORM

The Demographics and Contact Information Form serves to collect information regarding patient name, date of birth, race, ethnicity, phone number, and email address. This form will be completed at the screening visit. The purpose of obtaining this information is to obtain updated patient demographic and contact information for the study.

SCREENING VISIT QUESTIONNAIRE

The Screening Visit Questionnaire serves to collect information regarding HPV vaccination status, recruitment, employment, education, dependents, sexual life, tobacco usage, and alcohol usage. The purpose of obtaining this information is to characterize the subject population and to identify variables that may be associated with vaccine response.

ORAL WASH ANTIBIOTIC USAGE QUESTIONNAIRE

The Oral Wash Antibiotic Usage Questionnaire serves to collect information regarding patient antibiotic usage within the last 30 days, mouthwash usage, and details for oral wash collection sample. The purpose of obtaining this information is to aid in the interpretation of microbiome data as antibiotics are known to drastically alter them.

STOOL SAMPLE ANTIBIOTIC USAGE QUESTIONNAIRE

The Stool Sample Antibiotic Usage Questionnaire serves to collect information regarding patient antibiotic usage within the last 30 days. The purpose of obtaining this information is to aid in the interpretation of microbiome data as antibiotics are known to drastically alter them.

VISIT 9 QUESTIONNAIRE

The Visit 9 Questionnaire serves to collect information regarding patient experience such at the end of study treatment. The purpose of obtaining this information is to improve retention.

RECURRENCE QUESTIONNAIRE

The Recurrence Questionnaire serves to collect information regarding patient experience such at the end of study treatment. The purpose of obtaining this information is to improve retention.

EARLY TERMINATION QUESTIONNAIRE

The Early Termination Questionnaire serves to collect information regarding reasons why patients are withdrawing their participation on study prior to completion of study treatment. The purpose of obtaining this information is to improve retention.

